17. STATISTICAL CONSIDERATIONS

17.1. General Considerations

This section describes the general approaches planned to analyze the data from this study.

All efficacy and safety data will be displayed in subject data listings. Unless otherwise specified, Baseline is defined as the last observed measurement, whether scheduled or unscheduled, prior to study drug administration. All safety and efficacy endpoints will be summarized by dose level.

In general, categorical variables will be summarized by the frequency counts and percentages. Continuous variables will be summarized by the number of non-missing observations (n), mean, standard deviation (SD), median, minimum, and maximum values.

Unless otherwise specified, all statistical hypothesis testing will be two-sided using $\alpha = 0.05$.

Additional details of the planned analyses outlined here will be further described in the Statistical Analysis Plan.

17.2. Determination of Sample Size

The sample size for this study was determined from results of two previous studies. The first was a study in subjects with acute upper back, neck, or shoulder spasm and pain, which showed a difference of 0.4 in the average of Day 1 through Day 7 between the placebo and active groups, and SDs between 1.76 and 1.93 (across placebo and active groups respectively) (Collaku, 2017). A sample size of 400 subjects (80 per group) would provide at least 80% power to detect a difference of 0.9 between the placebo and treatment groups in the NRS scale, assuming a two-sample t-test at the 5% level of significance and a pooled SD of 2.0. This sample size assumes an effect size of 0.45 ($0.9/2.0 = 0.45$), using the formula $\text{Effect Size} = \text{Mean}/\text{SD}$, which is larger than that seen in the reference study but consistent with that seen in a second study.

A second previous study in subjects with acute musculoskeletal spasm associated with back pain showed effect sizes ranging from 0.57 to 0.62 for lumbar cinelgasia, based on a treatment difference of 9.6 at Day 3, with SDs of 15.5 (treated group) and 16.7 (placebo group) (Chandanwale, 2011). This study demonstrated effect sizes ranging from 1.1 to 1.6, based on a difference of 24.2 at Day 14 with SDs of 15.1 (treated group) and 23.0 (placebo group). The effect size of the current study is expected to be similar to that in Chandanwale, though sample size estimates have been made more conservative to provide sufficient power to detect smaller differences. Though the primary comparison of interest in this study is Day 14, the study is sufficiently powered to detect a treatment difference at Day 4 based on effect sizes ranging from 0.35 to 0.45.

The power for this range of effect sizes across six different scenarios for a test of linear trend, as well as a comparison between the high dose and placebo only, is provided below, assuming $n=80$ in each group. Assuming an effect size of 0.4 (averaging the lowest and highest effects sizes)

yields power estimates that are greater than 80% for each scenario tested, except when all treatment groups have identical differences from placebo.

Sample size considerations are provided in [Table 1](#).

Table 1 Sample Size Considerations

Effect Size (High Dose vs. Placebo)	Hypothesized Difference from Placebo				Power: Linear Contrast	Power: High Dose vs. Placebo
	Dose Group 1	Dose Group 2	Dose Group 3	Dose Group 4		
0.35	0	0	0.35	.35	84%	60%
	0	0	0.25	0.35	76%	60%
	0	0.08	0.25	0.35	76%	60%
	0	0.12	0.24	0.35	76%	60%
	0.08	0.16	0.24	0.35	68%	60%
	0.35	0.35	0.35	0.35	51%	60%
0.4	0	0	0.4	0.4	92%	71%
	0	0	0.2	0.4	81%	71%
	0	0.1	0.3	0.4	87%	71%
	0	0.13	0.26	0.4	85%	71%
	0.05	0.1	0.26	0.4	81%	71%
	0.1	0.2	0.3	0.4	81%	71%
	0.4	0.4	0.4	0.4	62%	71%
0.45	0	0	0.45	0.45	97%	81%
	0	0	0.23	0.45	89%	81%
	0	0.1	0.3	0.45	92%	81%
	0	0.14	0.28	0.45	91%	81%
	0.05	0.1	0.28	0.45	89%	81%
	0.11	0.22	0.33	0.45	88%	81%
	0.45	0.45	0.45	0.45	72%	81%

17.3. Analysis Populations

The analysis populations will be defined as follows:

- Intent-to-Treat (ITT) Population: All randomized subjects who receive any amount of study drug. This population will be used as the primary analysis population for all efficacy endpoints. Subjects will be included in this population based on their randomized treatment assignment.
- Safety Population: All subjects who receive any amount of study drug. This population will be used for all summaries of safety data. Subjects will be included in this population based on the actual treatment received.
- Per-Protocol (PP) Population: All randomized subjects who complete the study with no significant protocol violations that would affect the efficacy analyses. The

PP Population will be determined prior to database lock and will be used for sensitivity analyses on the primary and select secondary endpoints.

17.4. Statistical Analysis Methods

17.4.1. Disposition and Demographics

The number and percentage of subjects in each analysis population will be summarized. Subject disposition, including the number of subjects randomized, dosed, completing the Day 14 visit, and not completing the Day 14 visit by reason for withdrawal will be summarized for the ITT Population. Subject demographics and baseline characteristics will also be summarized for the ITT Population and will include age, sex, race, ethnicity, height, and weight.

17.4.2. Efficacy Analysis

17.4.2.1. Primary Efficacy Analysis

The primary efficacy endpoint is subject-rated pain “right now” due to acute back spasm using an NRS (0-10 scale, from no pain to worst possible pain) for the clinic visit on Day 14. This analysis will be performed using a linear test of trend across doses, using a mixed effect model for repeated measures. The model will include treatment and time as fixed effects, the treatment by time interaction, and the baseline NRS rating as a covariate. Differences in linear trend for each dose level versus placebo will be presented with 95% confidence intervals and associated p-values.

17.4.2.2. Secondary Efficacy Analyses

The analysis performed for the primary endpoint will be repeated for the NRS at Day 4.

In addition to the primary efficacy analysis, subjects will also use the NRS scale to record pain intensity due to back spasm each day on an outpatient basis. Ratings will be averaged for both morning and evening recordings on Days 1 through Day 14 and summarized by dose level and day using descriptive statistics. Mean NRS pain intensity scores will also be plotted in a line graph over time, with associated standard errors (SEs) for Days 1 through 14. The analysis will be repeated using the evening values only for NRS scores on rest and also on movement. The comparison of each group to placebo will be conducted using a mixed effects model as described for the primary analysis.

The SRMH and the Functionality Assessment: FFD will be analyzed using the same methods described for the primary endpoint.

Global symptom assessments (CGI and PGI) will be summarized by the percentage of subjects reporting each individual response. The proportion of subjects in each category will be recorded at each day. The comparison of each group to placebo will be conducted using a Wilcoxon Rank Sum test.

Quality of sleep will be analyzed using the same methods described for the global symptom assessments.

Median time (in hours) to relief of pain on Days 1 and 14 compared to baseline will be plotted using Kaplan-Meier (K-M) curves. Estimates of the median times will be presented along with

their associated 95% confidence interval (CI) in a corresponding table. Treatment group comparisons will be summarized with hazard ratios and their associated 95% CI from a Cox Proportional Hazards regression model with treatment as the main effect and p-values from the generalized Wilcoxon test.

Use of rescue medications will be summarized using frequency counts and percentages by generic drug name. Average daily use and total use will be tabulated using descriptive statistics. The Shapiro-Wilk test will be used to examine the assumption of normality. If this test is statistically significant (i.e., $p \leq 0.05$) then the assumption of normality is violated and the total rescue medication consumption will be analyzed using a Wilcoxon Rank Sum test. Results will be expressed as median (range) and p-values. However, if the assumption of normality holds (i.e., Shapiro-Wilk p-value > 0.05), then the total rescue medication consumption will be analyzed using an analysis of variance (ANOVA) model with randomized treatment as the main effect. Results will be expressed as means, SDs, and least squares mean difference (LSMD) and SEs with associated 95% CI, and p-values.

All other secondary endpoints will be summarized by dose using descriptive statistics. In addition, the comparison of each group to placebo will be conducted using an ANCOVA model, adjusting for baseline.

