8.2. Secondary Objectives

The secondary objectives of this study are:

- To assess the safety and tolerability of tolperisone in subjects with pain due to acute back spasm.
- To determine the onset of action of tolperisone in treatment of pain due to acute back spasm.
- To determine the duration of pain relief of tolperisone in treatment of pain due to acute back spasm.
- To determine the need for rescue medication when treated with various doses of tolperisone for pain due to acute back spasm.

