The number of subjects with relief and those censored will be summarized by treatment group for the ITT population. Estimates of the median times will be presented along with their associated 95% confidence intervals. Treatment group comparisons will be summarized with hazard ratios and their associated 95% CI from a Cox Proportional Hazards regression model with treatment as the main effect and p-values from a generalized Wilcoxon test.

The Kaplan Meier plots of time to pain relief by treatment group will be presented and display the subjects with relief and those censored at each study day.

A by subject listing of derived time to relief estimates will also be presented.

7.4.5.9 *Rescue Medication Use*

The use of study provisioned medication will be summarized using frequency counts and percentages for the number of tablets consumed by treatment group for the ITT population. Descriptive statistics will also be presented by treatment group. The number of days of medication use, average daily use (caplets/day of medication use) and total use will be tabulated using descriptive statistics. The frequency and percentage of subjects with rescue medication entry will be presented.

The Shapiro-Wilk test will be used to examine the assumption of normality for total rescue medication use across all dose groups. If this test is statistically significant (i.e., $p \leq 0.05$) then the assumption of normality is violated and the total rescue medication consumption will be analyzed using a Wilcoxon Rank Sum test.

However, if the assumption of normality holds (i.e., Shapiro-Wilk p-value > 0.05), then the total rescue medication consumption will be analyzed using an analysis of variance (ANOVA) model with randomized treatment as the main effect. The LSM and LSMD will be presented with associated 95% CI and p-values comparing each treatment group to placebo.

A data listing of rescue medication use will be presented and include the average number of tablets consumed and total number of tablets rescue medication consumed for each subject.

7.4.5.10 *Oswestry Disability Index*

ODI score (%) will be calculated as $(\text{total score} \times 2) / (\text{number of sections answered} / 10)$, rounded to the nearest integer, where the total score is the sum of the individual section scores.

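### A Shapiro-Wilk pre-test chooses the rescue-use analysis, and the branch it will probably choose has no planned difference from placebo and no confidence interval

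*Protocol*

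**What the plan says.** The need for rescue is a stated secondary objective (Protocol 8.2; repeated in SAP 5.2): "To determine the need for rescue medication when treated with various doses of tolperisone for pain due to acute back spasm".

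Protocol 17.4.2.2 sets a two-stage rule for total rescue consumption, starting with: "The Shapiro-Wilk test will be used to examine the assumption of normality".

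- **p ≤ 0.05:** Wilcoxon Rank Sum test. "Results will be expressed as median (range) and p-values".
- **p > 0.05:** ANOVA with treatment as main effect, reporting means, SDs and least squares mean differences with SEs, 95% CIs and p-values.

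SAP 7.4.5.9 keeps the rule and states what is tested: "The Shapiro-Wilk test will be used to examine the assumption of normality for total rescue medication use across all dose groups". Its least squares mean difference and 95% CI versus placebo appear only in the ANOVA paragraph, and the Wilcoxon paragraph names no estimate. SAP 7.7.1, which lists changes to the planned analyses, leaves the rule as it is.

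Apart from the pre-test, the SAP tabulates several items by arm: tablet counts and percentages, days of use, average daily use, total use, and the percentage of subjects with a rescue entry. SAP 7.1.1 fixes descriptive statistics as n, mean, SD, median, quartiles and range.

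**The concern.** A normality test at n near 400 detects departures far too small to harm a comparison of means. Total rescue use is an as-needed integer count with a floor at zero and a ceiling, so a departure from normality is close to built in. The SAP also tests the pooled raw totals rather than model residuals. A true dose effect, which makes the pooled data a mixture, would itself count against normality.

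Two things follow. First, the only branch with a between-group estimate is the one least likely to be reached. A trial meant to identify a Phase 3 dose would then have no planned statement of how many fewer rescue tablets each dose needs, or how precisely that is known. Second, if the pre-test happens to pass, the comparison moves from ranks to means, so the data decide what is estimated.

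**Working it through.** **Inputs.** Size of the trial: "A sample size of 400 subjects (80 per group) would provide at least 80% power" (Protocol 17.2). Pre-test threshold 0.05 (Protocol 17.4.2.2, SAP 7.4.5.9). Rescue limit 3 per day (Protocol 7.3.2 and 14), with none on Days 4 and 14 (Protocol 14). One site's data are excluded (SAP 7.7.2); the number of subjects is not given, so n = 360 is run as an assumption. The distribution of total rescue use is not given, so a range of shapes is assumed.

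**Step 1: the plan's own figure.** The documents give no figure for rescue use. The sample size behind n = 400 can be reproduced. Power = Φ(d·√(n/2) − 1.96) with n = 80 per arm:
- d = 0.45: 0.45 × 6.325 = 2.846; Φ(0.886) = 81.2% (Protocol Table 1: 81%)
- d = 0.40: 2.530; Φ(0.570) = 71.6% (Table 1: 71%)
- d = 0.35: 2.214; Φ(0.254) = 60.0% (Table 1: 60%)

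The n of 400 is sound for the pain score. It was not set for rescue use.

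**Step 2: range of the count.** 14 − 2 = 12 permitted days; 12 × 3 = 36 tablets. Without the two excluded days it would be 14 × 3 = 42. The limit is approximate, because visits have windows (Protocol 10.1) and the bottle holds 50 caplets (Protocol 13).

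**Step 3: how often the pre-test rejects.** Shapiro-Wilk at p ≤ 0.05 on simulated integer totals from 0 to 36, 2,000 runs per cell:

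| Assumed shape | n = 400 | n = 360 | n = 80 |
|---|---|---|---|
| 50% structural zeros, else negative binomial mean 10, size 1 | 100% | 100% | 100% |
| 30% structural zeros, else negative binomial mean 10, size 2 | 100% | 100% | 100% |
| Negative binomial mean 8, size 1 | 100% | 100% | 100% |
| Negative binomial mean 12, size 5 | 100% | 100% | 87% |
| Poisson mean 12 | 100% | 99.9% | 29% |
| Rounded normal mean 12, SD 8, clipped at the bounds | 100% | 100% | 51% |
| Beta-binomial (3,3), symmetric | 98.9% | 97.3% | 16% |
| Rounded normal mean 18, SD 4 | 89% | 79% | 12% |
| Beta-binomial (5,5), symmetric | 74.5% | 66% | 7.6% |
| Rounded normal mean 18, SD 6 | 22% | 16% | 5% |

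The n = 80 column matters only if the test were run within arms (the protocol does not say; the SAP pools) or if many subjects without diary entries were dropped. Zero-heavy and strongly skewed counts still reject in 87–100% there.

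**Step 4: what each branch yields.** Wilcoxon branch: p-values beside per-arm summaries, with no planned contrast. ANOVA branch: a contrast with a 95% CI. Medians alone can conceal a difference. With an assumed 55% non-users and 30% lower use among users, the two arm medians were identical in 82% of simulated trials.

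**Step 5: what an interval would show.** Half-width for a difference in means, 80 per arm: 1.96 × SD × √(2/80) = 0.310 × SD. That is ±1.55 tablets at SD 5, ±2.5 at SD 8, ±3.1 at SD 10 and ±3.7 at SD 12 (SDs assumed). In simulation with skewed, zero-heavy counts at 80 per arm, the unequal-variance interval had 95% coverage, so non-normality is no reason to withhold it.

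**The case against.** The strongest reply has four parts.

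**The size of the effect is not hidden.** A reader might infer that the objective is answered by four p-values and nothing else. The SAP does not support that: means, SDs, medians, tablet frequencies, days of use and user percentages appear by arm in both branches. A crude difference and interval could be worked out from them. This stands, and it narrows the point to the absence of a planned contrast with its interval. The general SAP 7.1.1 rule of 95% CIs for point estimates does not fill the gap, because the Wilcoxon branch names no point estimate.

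**The test is valid and prespecified.** A reader might infer inflated type I error. Nothing in the documents shows it: the rule and both branches are fixed, and the SAP is to be finalised before unblinding (SAP 4). If Wilcoxon is nearly certain, the plan is in effect a fixed rank test, a reasonable choice for skewed counts. This also stands. The more certain the rejection, the less the switch matters and the more the missing contrast does.

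**A loss of power is not established.** A baseline-adjusted count model beat the rank test under one set of assumed inputs (60–66% against 49–53%) and under another (48–50% against 35–41%). The dispersion and the link to baseline pain were assumed, and the data favoured the model's own family. Adding baseline NRS moved count-model power by only about 0 to 6 points. The point does not rest on power.

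**Other endpoints also get Wilcoxon p-values alone** (medication helpfulness, global impressions, sleep, daily activities; SAP 7.4.5). True, but those are ordinal ratings. Rescue use is a count in natural units, tied to its own stated objective, and the plan already provides an estimate for it in one branch.

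**Conclusion.** The point holds in a limited form. Under any plausible skewed or zero-heavy shape, the pre-test will reject at n near 400. The need-for-rescue objective will then be reported through per-arm descriptive statistics and p-values, with no planned difference from placebo and no confidence interval. This rests on an assumed distribution, since the documents give none. It would weaken only if totals formed a symmetric bell well inside the 0–36 range, which is unlikely for as-needed medication. The exact n (site exclusion, missing diary entries) does not change it: at n = 360 every case that rejected in all or nearly all trials at n = 400 stays at 97% or above.

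The documents do not support reading this as an invalid test, as the absence of any measure of effect, or as a threat to the primary conclusion. It is a minor point on one secondary endpoint, and a cheap improvement.

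**What to change.** Delete the Shapiro-Wilk step from Protocol 17.4.2.2 and SAP 7.4.5.9 and name one analysis in advance.

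- **Estimate:** for each dose versus placebo, always report the difference in mean rescue tablets with a 95% CI (unequal-variance or bootstrap). Keep the Wilcoxon p-value beside it.
- **Unequal follow-up:** use tablets per diary day, or an equivalent allowance, so that early dropouts do not count as needing less rescue. State how missing diary days are handled. The SAP's existing average daily use is per day of medication use, so it does not serve this purpose.
- **Acceptable alternative:** a log-link count model with robust SEs, a days-at-risk offset and baseline NRS, reporting dose-to-placebo ratios with 95% CIs. The choice between this and a difference in means is partly preference.
- **Avoid:** relying on the Hodges-Lehmann shift. With many non-users it is often exactly 0. With 40% zeros and means of 10 against 7 among users (assumed), it was 0 in 94% of 800 simulated trials.

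Cost: a few lines of wording and one extra estimate per dose. No new data are needed, since daily rescue entries and baseline NRS are already collected.

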17.4.2.3. Handling of Dropouts or Missing Data

Efficacy analyses on the ITT Population will use the last observation carried forward (LOCF) method for handling missing data. Only post-baseline values will be carried forward. Efficacy analyses on the ITT Population will also be performed using observed data only. All other analyses will be based on observed data only.

17.4.3. Safety Analysis

Safety analysis will be based on all subjects randomized who receive at least one dose of the study drug. The safety analysis will evaluate adverse events and additional safety parameters.

Additional safety parameters will be assessed from summaries of physical examinations, 12-lead ECGs and vital signs.

17.4.3.1. Adverse Events

Adverse events will be summarized by dose level. All adverse events will be coded from the verbatim text to the lower level term and mapped to preferred term and primary system organ class using the latest version of MedDRA. The number and percentage of subjects experiencing at least one AE will be summarized by body system, preferred term, and dose level. If appropriate, AEs will also be summarized by severity and relationship to study drug. Serious AEs, if any, will be tabulated. Summaries that are displayed by system organ class and preferred terms will be ordered by descending incidence of system organ class and preferred term within each system organ class. Summaries displayed by preferred term only will be ordered by descending incidence of preferred term.

Summaries of the following types will be presented:

- Overall summary of number of unique TEAEs and treatment-emergent SAEs and subject incidence of TEAEs meeting various criteria;

- Subject incidence of TEAEs by MedDRA system organ class and preferred term;
- Subject incidence of TEAEs by severity, MedDRA system organ class, and preferred term;
- Subject incidence of TEAEs by relationship to study drug, MedDRA system organ class, and preferred term;
- Subject incidence of SAEs by MedDRA system organ class and preferred term.

Adverse events will also be presented in subject listings. The duration of AEs will be determined and included in listings, along with the action taken and outcome.

17.4.3.2. Extent of Exposure to Study Drug

The total amount of study drug used by each subject as well as the mean daily amount of study drug used by each subject will be calculated. Total amount and mean daily amount of study drug will be summarized by dose level using descriptive statistics.

17.4.3.3. Clinical Laboratory

Clinical laboratory results and changes from baseline will be summarized by dose using descriptive statistics for all regularly scheduled visits. For each laboratory test, individual subject values will be listed and values outside of the standard reference range will be flagged. A separate listing will be provided to include all clinical laboratory values outside normal range (including Screening/Baseline Visit 1 and Day 14/ EOT examination) and will also include relevant demographic information.

17.4.3.4. Vital Signs

Vital sign (blood pressure, heart rate, respiratory rate, and body temperature) measurements and changes from baseline will be summarized by dose using descriptive statistics for regularly scheduled visits. Measurements will also be presented in a subject data listing.

